### 6.2.3. Feasibility

As defined in the protocol, the secondary endpoints for assessment of the feasibility of self-management of treatment intake, or with the assistance of the caregiver under recommended conditions are the following for patients treated on an outpatient basis:

- Patients who temporarily discontinued their treatment (yes/no)
- Patients who prematurely (i.e. prior to Day 10) discontinued their treatment (permanent interruption) (yes/no)
- Patients who delayed starting treatment (i.e. date of D1 – date of D0 > 1 day) (yes/no)
- Patients who mislaid treatment units (i.e. number of tablets left over > 0) (yes/no)
- Patients who were hospitalized during their treatment period
- Patients with:
  - 1, 2, 3, ..., 9, 10 days of treatment administration performed at the hospital.
  - 0 days (=treatment administration performed at home only).
- Patients who took treatment regularly, according to the patients themselves (=questionnaire on Day 11: Question 5 “How did you take your treatment?”) (yes/no)
- Patients who understood the instructions concerning the dosing regimen of fexinidazole (=questionnaire on Day 0: patients who correctly answered to the 8 questions) (yes/no)
- Patients who complied with the dosing regimen, including intake of treatment during a meal (=questionnaire on Day 11: patients who correctly answered to the 4 questions 5.1 to 5.4) (yes/no)

In addition, the following data will be listed:

- Reasons of temporary treatment discontinuation
- Reasons of premature and permanent treatment discontinuation
- Reasons of hospitalization during the treatment period

The following data will also be described in patients treated in hospital:

- Patients who temporarily discontinued their treatment (yes/no)

- Patients who prematurely discontinued their treatment (permanent interruption) (yes/no)

The following data will also be listed in patients treated in hospital:

- Reasons of temporary treatment discontinuation
- Reasons of premature and permanent treatment discontinuation

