6.1. Timing of Assessments

Study procedures will be performed in accordance with the following schedule (see also Table 2 – Theoretical Schedule of Visits and Acceptable Leeway):

Day -15 to Day -1: screening and baseline assessment

Then, depending on the type of patient:

Patients treated in hospital:

Treatment period: Day 1 to Day 10

EoT visit: Day 11

■ EoH visit: between Day 13 and Day 18

Patients on an out-patient basis:

IMP dispensing visit prior to first intake of IMP: Day 0

Compulsory EoT visit at investigational centre: Day 11

Out-patient follow-up visits for all patients:

• 3 months, 6 months, 12 months and 18 months

The schedule of visits is calculated from the first day of treatment (Day 1).

Confidential Page 32 of 83

Table 2 - Theoretical Schedule of Visits and Acceptable Leeway

Type of Visit	Schedule of Visits and Acceptable Time Window	Acceptable leeway*
EoT Visit	Day 11	Day 11 + 1 day
End-of-Hospitalisation Visit, only for patients treated in hospital	Between Day 13 and Day 18	Day 18 at the latest
3-month follow-up visit	3 months ± 1 week after Day 1	2 to 4 months, i.e. 60 to 149 days, after Day 1
6month follow-up visit	6 months ± 1 week after Day 1	5 to 9 months, i.e. 150 to 299 days, after Day 1
12-month follow-up visit	12 months ± 4 weeks after Day 1	10 to 16 months, i.e. 300 to 509 days, after Day 1
18-month follow-up visit	18 months ± 4 weeks after Day 1	17 to 21 months, i.e. 510 to 659 days, after Day 1

^{*} The acceptable leeway for the visit starts on the first day of the period mentioned and ends on the last day of the period mentioned.

Additional unscheduled visits may take place and must be recorded in the CRF. See also Appendix 7 - Schedule of Study Events (p 82).

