8.1. Temporary Interruption of Treatment

Patients treated on an out-patient basis must not under any circumstances discontinue treatment, even temporarily. However, if temporary interruption of treatment seems inevitable, the patient must contact the Investigator or come to the investigational centre before interrupting treatment. The Investigator will decide on the appropriate course of action and will inform the Sponsor as quickly as possible.

Temporary interruption of treatment will not necessarily lead to patient withdrawal from the study. In some cases, treatment may be interrupted for a maximum of one day, i.e. one missed dose of fexinidazole, and treatment will therefore be delayed. Treatment may be reintroduced at the discretion of the Investigator. One additional day of treatment will be added to make up for the missed dose, and the EoT visit will take place on Day 12. The patient should continue the visits and study procedures as planned, taking into account the delay. The reasons for interrupting treatment must be recorded in the CRF.

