9.6.3. Secondary Analysis - Feasibility

The secondary analyses concerning the feasibility of patient self-management of treatment intake under recommended conditions will be performed on the subgroup of out-patients from the ITT population, i.e. all patients who were considered as eligible for treatment on an out-patient basis and to whom the IMP was dispensed, regardless of whether or not they took the IMP. The endpoints analysed will be as follows:

- Number and proportion of patients who temporarily interrupted treatment;
- Number and proportion of patients who prematurely discontinued treatment;
- Number and proportion of patients who delayed starting treatment;
- Number and proportion of patients who mislaid treatment units;
- Number and proportion of patients who were hospitalised for reasons related to non-compliance.

Confidential Page 51 of 83

For each of the endpoints, the proportion of patients will be presented with the 95% Confidence Interval (CI).

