## 5. ANALYSIS SETS AND SUBGROUPS

The analysis sets are the following.

- **Screened HAT positive patients:** all HAT positive patients who signed the informed consent.
- **Intent-to-treat (ITT) population:** all patients included in the study, regardless of whether or not they took the IMP (but the treatment unit was provided to the outpatient);
- **Modified intent-to-treat (mITT) population:** all patients who took at least one tablet of fexinidazole;
- **Evaluable patients:** patients included in the mITT and excluding:
  - Patients lost to follow-up at 18 months (for primary efficacy endpoint and secondary efficacy outcome at 18 month), patients lost to follow-up at 12 months (for secondary efficacy outcome at 12 month), except those who were a failure before being lost to follow-up.
  - Patients with no post-treatment lumbar puncture
  - Patients who died for reasons clearly unrelated to efficacy or safety or disease evolution (\*\*).
- **Per protocol (PP):** all patients who completed the study in accordance with the protocol with no major violations (cf. [Section 8.2](#)) that could interfere with the efficacy evaluation. An out-patient who did not take any tablet of the IMP or with a compliance below 75% of the expected number of tablets is not per protocol unless it is due to lack of tolerance. Premature withdrawal from the study due to treatment inefficacy or intolerance will not be considered as a protocol violation.

Two study cohorts are defined:

- **Inpatients:** patients treated in hospital,
- **Outpatients:** patients treated on an outpatient basis. Note that outpatients that would require hospitalization (for any reason) will be analyzed according to their initial cohort (i.e. as “outpatients”).

The following subgroups are defined according to the stage and severity of disease at inclusion:

- Stage 1
- Intermediate stage
- Stage 1 + Intermediate stage
- Stage 2
- WBC in CSF  $\leq$  100 /  $\mu$ L
- 100 < WBC in CSF  $\leq$  400 /  $\mu$ L
- WBC in CSF  $>$  400 /  $\mu$ L

For the analysis, these subgroups will be calculated as described in Table 1. Subgroups analyses are specified in [Section 8](#).

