### 6.3. Safety endpoints

As defined in the protocol (Section 2.2.2), the secondary endpoints for the assessment of the safety of fexinidazole will be:

- Occurrence of grade  $\geq 3$  adverse events (AEs), including laboratory and haematological abnormalities (if considered clinically significant), between the first intake of fexinidazole and the end of the observation period\* or the follow-up period (18 months) for non-serious AEs assessed as related to fexinidazole.
- Occurrence of any serious adverse event (SAE) between the first intake of fexinidazole and the end of the follow-up period (18 months).
- Number of patients who prematurely discontinued treatment (i.e. prior to Day 10) or were hospitalised for reasons related to safety\*\* (e.g. including overdose).

\* The observation period extends from the first intake of fexinidazole on Day 1 until the end-of hospitalisation visit (between Day 13 and Day 18) for patients treated in hospital. For outpatients, the observation period extends to the end-of-treatment visit on Day 11.

\*\* A patient will be considered as “hospitalised for reasons related to safety” if he/she experienced a SAE during the treatment period and he/she was initially planned to be treated as an outpatient and he/she was hospitalized during the treatment period.

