#### 8.7.4. Feasibility

The secondary analyses concerning the feasibility of patient self-management of treatment intake under recommended conditions will be performed on outpatients from the ITT population. The endpoints analysed will be those defined in [Section 6.2.3](#). For each of the endpoints, the proportion of patients will be presented with the 95% CI.

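### SAP 6.2.3: an out-patient who never starts enters neither the delayed-start nor the early-stop count, and the Day 10 cut conflicts with the make-up dose in Protocol 8.1

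*SAP*

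**What the plan says.** Protocol 2.2.4 and 9.6.3 name delayed start and premature discontinuation as feasibility endpoints and attach no cut-off to either. Protocol 9.6.3 has simply "Number and proportion of patients who prematurely discontinued treatment". SAP 6.2.3 says it follows the protocol but adds operational rules: "Patients who delayed starting treatment (i.e. date of D1 – date of D0 > 1 day) (yes/no" and "Patients who prematurely (i.e. prior to Day 10) discontinued their treatment (permanent interruption) (yes/no".

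Under SAP 8.7.4 the feasibility analyses "will be performed on outpatients from the ITT population". SAP Section 5 defines that set as patients included "regardless of whether or not they took the IMP (but the treatment unit was provided to the outpatient". Day 1 is the first day of treatment: "The schedule of visits is calculated from the first day of treatment (Day 1".

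Protocol 8.1 allows one missed dose to be made up: "One additional day of treatment will be added to make up for the missed dose, and the EoT visit will take place on Day 12". Under that rule the last planned dose falls on Day 11.

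The Day 10 cut reappears in the safety endpoint of SAP 6.3, "Number of patients who prematurely discontinued treatment (i.e. prior to Day 10", where Protocol 2.2.2 has none.

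**The concern.** Whether patients can manage treatment at home is a stated secondary objective. The ITT out-patient denominator was chosen so that those who took nothing stay in. Yet the two rows that describe a failure to begin or to finish both presuppose that treatment began. A never-starter is therefore either missing or counted as 'no' in them.

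The early-stop rule has a separate fault. It fixes a calendar day although the protocol lets the course run one day longer. SAP 6.2.2 recognises this: it sums tablets to Day 11 and treats a patient who made up a missed dose as a completer. The early-stop rule was not adjusted to match.

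At stake are two reported proportions and their 95% intervals, and the clarity of one safety endpoint.

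**Working it through.** No stated figure needs reproducing here; the check applies the SAP rules literally to dosing patterns. Planned tablets follow from Protocol 5.1: 3×4 + 2×6 = 24, and 2×4 + 1×6 = 14 for children below 35 kg, as in SAP 6.2.2. (SAP 8.5 gives 12 for these children; those passages must be reconciled.) The SAP does not say which date makes a stop 'prior to Day 10', so two readings are tested: A, last intake before Day 10; B, first missed dose before Day 10.

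| Pattern | Tablets taken | Early stop, A | Early stop, B | Other rows that register it |
|---|---|---|---|---|
| Never starts, pack returned | 0 | no | no | left-over tablets; full course = no; compliance 0% |
| Stops after Day 4 | 12/24 (50.0%) or 8/14 (57.1%) | yes | yes | left-over tablets; full course = no |
| Days 1–9 taken, Day 10 omitted | 22/24 (91.7%) or 13/14 (92.9%) | yes | no | left-over tablets; full course = no |
| One dose missed, resumed, Day 11 make-up omitted | 22/24 (91.7%) or 13/14 (92.9%) | no | no | temporary discontinuation; left-over tablets; full course = no |
| One dose missed, make-up taken | 24/24 or 14/14 | no | no | temporary discontinuation only, as intended |

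1. **Never-starter.** With no Day 1, the difference D1 − D0 does not exist, so delayed start cannot be 'yes'. With nothing begun, nothing was discontinued. If the pack comes back, the tablet-based row in 6.2.3 that registers the patient is left-over tablets, which the SAP labels as mislaid units. If the patient is interviewed, the two Day 11 questionnaire items may also be negative. If there are no Day 11 data, all of these may be missing, and SAP 7.6 has no missing-data rule for feasibility.

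2. **Omitted make-up dose.** The last intake is on Day 10 and the first dose missed for good is on Day 11. Neither is before Day 10, so the patient is not premature on either reading.

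3. **Omitted Day 10 dose.** The answer changes with the reading.

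4. **Consistency.** The cut is absent from Protocol 2.2.2, 2.2.4 and 9.6.3, from the in-patient item in SAP 6.2.3, and from SAP 6.3.4 and 8.8.1. SAP Section 11 does not list it.

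**Size, for illustration only.** Assume 40, 80 or 120 out-patients among the 174 planned. Assume 2 early stops are counted, and k = 1 to 5 others never started or omitted the make-up dose. The share who did not begin or did not finish moves from 2/N to (2 + k)/N. Intervals are Clopper-Pearson: lower limit = Beta quantile 0.025 with parameters (x, N − x + 1); upper limit = Beta quantile 0.975 with (x + 1, N − x).

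| N (assumed) | Shown, 2/N | k = 1 | k = 5 |
|---|---|---|---|
| 40 | 5.0% (0.6–16.9) | 7.5% (1.6–20.4) | 17.5% (7.3–32.8) |
| 80 | 2.5% (0.3–8.7) | 3.8% (0.8–10.6) | 8.8% (3.6–17.2) |
| 120 | 1.7% (0.2–5.9) | 2.5% (0.5–7.1) | 5.8% (2.4–11.6) |

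**The case against.** These patients do not vanish. A never-starter who returns the pack is 'yes' for left-over tablets. The disposition table has included and treated counts in an out-patient column, so their difference shows who took nothing. SAP 6.2.2 and 8.7.3 report full course, exact tablet count and overall compliance in the ITT, and list every patient who departs from the planned tablets or days. The omitted make-up dose already counts as a temporary discontinuation. Safety stops at the last dose are caught without a day cut in SAP 6.3.4, 8.8.1 and 8.8.2. The Day 11 visit is compulsory, the pack must be returned, non-attenders must be pursued, and out-patients live within an hour of the centre, so patients with no Day 11 data may be few. The endpoints are descriptive and drive no decision.

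All of this stands, and it limits the reach of the point. A reader might infer that failures of home treatment are understated as a whole, that never-starters appear in no feasibility row, or that late safety stops are lost. The documents support none of these. What the objection does not do is correct the two rows the protocol names. Left-over tablets under the label of mislaid units do not tell a reader that treatment was never begun, and a temporary discontinuation does not tell a reader that the course was never finished.

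**Conclusion.** The point holds for two feasibility rows in SAP 6.2.3 and for the safety endpoint as worded in SAP 6.3. A never-starter can enter neither the delayed-start nor the early-stop numerator. A patient who omits the make-up dose is not an early stop on either reading. A patient who omits the Day 10 dose is classified by a date the SAP leaves unstated. The SAP cut and Protocol 8.1 need to be reconciled.

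The direction favours home treatment. The size is unknown: the out-patient numbers and event counts in the illustration are assumptions, and if nobody fits these patterns nothing changes. This is a definition fault worth correcting, not evidence that the feasibility results as a whole are wrong.

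**What to change.** In SAP 6.2.3:

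- Report 'never started' as its own row over all ITT out-patients, separate from 'delayed start', and state how a missing Day 1 date is handled.
- Define 'prematurely discontinued', for analysis, as permanent cessation before all planned daily doses, including any make-up dose, had been taken, whatever the calendar day. Use the same definition for in-patients and in SAP 6.3.
- Show the number of Day 11 non-attenders and of missing values beside each proportion. Do not score non-attenders as failures on every item: someone known to have started on time would then be counted as delayed, which creates an upward bias.
- Record the change in SAP Section 11 as made after database lock, alongside the post-lock change already there.

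The cost is a few lines of SAP text and a little reprogramming of derived variables, with no new data. Feasibility rates may look slightly less favourable.

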- Occurrence of grade ≥ 3 adverse events (AEs), including laboratory and haematological abnormalities (if considered clinically significant), between the first intake of fexinidazole and the end of the observation period* or the follow-up period (18 months) for non-serious AEs assessed as related to fexinidazole. AE severity will be graded according to the National Cancer Institute (NCI) Common Toxicity Criteria for AEs (CTCAE), Version 4.03 (14) and, for certain laboratory parameters, modified CTCAE will be used.
- Occurrence of any serious adverse event (SAE) between the first intake of fexinidazole and the end of the follow-up period (18 months).
- Number of patients who discontinued treatment or were hospitalised during treatment for reasons related to safety, including overdose.
 - * The observation period extends from the first intake of fexinidazole on Day 1 until the end-of-hospitalisation visit (between Day 13 and Day 18) for patients treated in hospital. For out-patients, the observation period extends to the end-of-treatment visit on Day 11.

Treatment Compliance in Out-patients

Presence of fexinidazole and/or its metabolites in the blood sample collected on Day 11 and/or at any unscheduled visit between Day 1 and the EoT visit, number of patients who brought unused tablets back at end of treatment, number of tablets brought back at the end of treatment (D11) and patients' responses to the questionnaire at the compliance interview.

Feasibility of Out-patient Treatment

On the basis of examination of packaging at the end of treatment and on interview with patients and/or the caregiver: number of patients who temporarily interrupted treatment, number of patients who prematurely discontinued treatment, number of patients who delayed starting treatment, number of patients who mislaid treatment units, number of patients who were hospitalised during treatment for reasons related to non-compliance, number of patients who took treatment regularly, according to the patients themselves, number of patients who understood the instructions concerning the dosing regimen of fexinidazole (questionnaire on Day 0), number of patients who complied with the dosing regimen (questionnaire on Day 11).

Confidential Page 13 of 83

Acceptability of Packaging in Out-patients

Questionnaire on Day 0 and Day 11 (patients and/or caregivers*)

Pharmacokinetics (PK) Parameters in Patients Treated in Hospital

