2.2.3. Secondary Endpoints - Compliance

The secondary endpoints for the assessment of compliance with treatment in patients treated on an out-patient basis will be:

- Presence of fexinidazole and/or its main metabolites in the blood sample collected on Day 11 and/or at any unscheduled visit between Day 1 and the end-of-treatment (EoT) visit;
- Number of patients who brought unused tablets back at the end of treatment;
- Number of tablets brought back at the end of treatment (D11)
- Patients' responses to the questionnaire at the compliance interview.

Confidential Page 24 of 83

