2.2.4. Secondary Endpoints - Feasibility

In patients treated on an out-patient basis, the secondary endpoints for assessment of the feasibility of self-management of treatment intake, or with the assistance of the caregiver* under recommended conditions, will be:

- Number of patients who temporarily interrupted treatment;
- Number of patients who prematurely discontinued treatment;
- Number of patients who delayed starting treatment;
- Number of patients who mislaid treatment units;
- Number of patients who were hospitalised during treatment for reasons related to non-compliance;
- Number of patients who took treatment regularly, according to the patients themselves (compliance interview at Day 11);
- Number of patients who understood the instructions concerning the dosing regimen of fexinidazole (questionnaire on Day 0);
- Number of patients who complied with the dosing regimen, including intake of treatment during a meal (questionnaire on Day 11).
- * Caregiver definition: accompanying person designated to take care of the patient during the treatment period and, more specifically, to ensure that fexinidazole is taken according to instructions. If several persons accompany the patient, a choice must be made by the patient (if possible) together with the Investigator to designate the most suitable person to fulfil the role.

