If the patient was treated on an out-patient basis, the following procedures will be performed:

- Interview for collection of AEs observed by the patient during the treatment period and collection of concomitant medication;
- Interview for compliance with accountability of fexinidazole tablets;
- Questionnaire to assess acceptability of packaging of IMP.

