#### 6.2.2. Compliance

As defined in the protocol, the secondary endpoints for the assessment of compliance with treatment in patients treated on an outpatient basis will be:

- Presence of fexinidazole and/or its main metabolites in the blood sample collected on Day 11 and/or at any unscheduled visit between Day 1 and the end-of-treatment (EoT) visit (*note: this endpoint will be analyzed by [REDACTED]*)
- Patients who had tablets left over at the end of treatment (i.e. number of tablets returned on day 11 > 0) (yes/no)
- Number of tablets left over at the end of treatment (i.e. number of tablets returned on day 11) (0, 1, 2, ...)
- Patients' responses to the questionnaire at the compliance interview on Day 11: Questions 5, 5.1, 5.2, 5.3 and 5.4.

In addition, the following endpoints will be assessed on all patients (i.e. inpatients and outpatients):

- Patients who completed the full course of treatment (i.e. at least 10 days) (yes/no)
- Patients fully compliant (i.e. children with body weight less than 35 kg who took exactly 14 tablets or children with body weight who took exactly 24 tablets or adults who took exactly 24 tablets) (yes/no)
- Patients who always took their treatment during a meal (yes/no)
- Patients who had at least one re-administration (yes/no)

- Patients who had at least one re-administration due to vomiting (yes/no)
- Patients who had at least one re-administration due to other reason (yes/no)
- Number of re-administration(s) by patient (0, 1, 2, ...)
- Overall compliance defined as:

- For patients with body weight < 35 kg (Children):

$$\text{Compliance (\%)} = \frac{100 \times \text{Actual dose taken (mg)}}{8400 \text{ mg (i.e. } 1200 \text{ mg} \times 4 \text{ days} + 600 \text{ mg} \times 6 \text{ days)}}$$

- For patients with body weight ≥ 35 kg (Children) or Adults:

$$\text{Compliance (\%)} = \frac{100 \times \text{Actual dose taken (mg)}}{14400 \text{ mg (i.e. } 1800 \text{ mg} \times 4 \text{ days} + 1200 \text{ mg} \times 6 \text{ days)}}$$

Note for overall compliance:

*Actual dose taken (mg) = 600 mg X number of tablets taken*

*Number of tablets taken = (sum of tablets taken from Day 1 to Day 11) + (sum of tablets taken for re-administration from D1 to D11)*

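### SAP 6.2.3 scores 'mislaid treatment units' as tablets returned on Day 11, so the row duplicates a compliance endpoint and loss by itself never triggers it

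*SAP*

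**What the plan says.** The protocol lists two separate out-patient endpoints. Section 2.2.3 (compliance) has "Number of patients who brought unused tablets back at the end of treatment". Section 2.2.4 (feasibility) has "Number of patients who mislaid treatment units", and section 9.6.3 repeats it for analysis as "Number and proportion of patients who mislaid treatment units". The Protocol Summary gives the source for the feasibility endpoints: "On the basis of examination of packaging at the end of treatment and on interview with patients and/or the caregiver". Section 6.6 schedules a matching Day 11 procedure for out-patients, "Interview for compliance with accountability of fexinidazole tablets", and section 5.4 requires the pack to be brought back at that visit.

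SAP 6.2.3 states that its feasibility endpoints follow the protocol, and then gives the rule "Patients who mislaid treatment units (i.e. number of tablets left over > 0) (yes/no". SAP 6.2.2 contains the compliance endpoint "Patients who had tablets left over at the end of treatment (i.e. number of tablets returned on day 11 > 0) (yes/no", and its next item gives the number of tablets left over the same meaning. SAP 8.7.3 analyses the compliance endpoint, and SAP 8.7.4 the feasibility endpoint, in out-patients of the ITT population. SAP 8.7.4 adds a 95% CI. The planned outputs are Tables 2.2.3.1 and 2.2.4.1. SAP 11 lists the departures from the protocol, and this rule is not among them.

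**The concern.** A mislaid tablet cannot be handed back. A rule that counts tablets handed back therefore measures something other than loss, and in many patients its opposite. Whether patients can manage treatment at home is a secondary objective of the study, and losing part or all of the supply is one of the ways in which home treatment can fail. As written, the feasibility table will show a proportion and a 95% CI under the name of loss that is really the proportion who returned tablets. A reader comparing the two tables would see the same count twice and could take it as two findings that agree.

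**Working it through.** **Inputs.** The regimen is in Protocol 5.1, the pack content (one 10-day course) in Protocol 5.3, the definitions in SAP 6.2.2 and 6.2.3, and the analysis sets in SAP 8.7.3 and 8.7.4.

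**Tablets per course.** At 35 kg or above: 3 × 4 + 2 × 6 = 24, and 24 × 600 mg = 14400 mg. Below 35 kg: 2 × 4 + 1 × 6 = 14, and 14 × 600 mg = 8400 mg. Both totals reproduce the denominators in SAP 6.2.2.

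**Rules.** Let D be tablets dispensed, T tablets taken and R tablets returned on Day 11, with no tablets from outside the pack.

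- SAP 'mislaid' flag: yes if R > 0.
- SAP 'left over' flag: yes if R > 0.
- Tablets lost, if every untaken and unreturned tablet was lost: D − T − R.

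The first two rules are the same function in the same patients, so their counts and percentages must agree. No assumption about the data is needed for that.

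**Cases.**

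| Patient | D | T | R | D − T − R | SAP 'mislaid' |
|---|---|---|---|---|---|
| All taken | 24 | 24 | 0 | 0 | no |
| 4 lost, rest taken | 24 | 20 | 0 | 4 | no |
| 4 returned, none lost | 24 | 20 | 4 | 0 | yes |
| Pack lost before Day 1 | 24 | 0 | 0 | 24 | no |
| Pack lost after Day 4 | 24 | 12 | 0 | 12 | no |
| Stopped after Day 4, rest returned | 24 | 12 | 12 | 0 | yes |
| 2 lost and 2 returned | 24 | 20 | 2 | 2 | yes |
| Below 35 kg, pack lost after Day 4 | 14 | 8 | 0 | 6 | no |

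For a lost pack, R might be recorded as missing rather than 0. The SAP gives no rule, but the flag is not yes in either case.

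**All combinations.** Every pair (T, R) with T + R ≤ D was enumerated. These are counts of possibilities, not probabilities.

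| | D = 24 | D = 14 |
|---|---|---|
| Loss, nothing returned: flag no | 24 | 14 |
| Loss, something returned: flag yes | 276 | 91 |
| No loss, something returned: flag yes | 24 | 14 |
| No loss, nothing returned: flag no | 1 | 1 |

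A patient with losses scores yes only when other tablets come back, and then it is the returned tablets that set the flag.

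**Effect on the reported proportion.** If x of n out-patients lose tablets and return none, and y return tablets and lose none, the reported proportion differs from the true one by (y − x)/n. The error can go in either direction, and it can cancel in the total while individual patients are still misclassified.

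**Expected tablets below 35 kg.** SAP 6.2.2 and 8.7.3 use 14, while SAP 8.5 labels the same group with 12. The 12 enters no formula.

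**The case against.** Several points on the other side stand.

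- **Loss is not invisible.** SAP 6.2.3 also counts premature permanent discontinuation, with a 95% CI in the same table, and lists the reasons. A patient whose pack is lost after Day 4 and not replaced stops before Day 10 and would appear there. That patient would also fail the full-course and fully-compliant endpoints of SAP 6.2.2 and enter the SAP 8.7.3 listing. Protocol 5.4 adds reconciliation of used and unused quantities by the monitors.
- **Some patients with losses do score yes**, namely those who also return tablets.
- **The intended meaning is not fully fixed.** Neither document defines a treatment unit. The ITT definition in SAP 5 uses the singular for what the out-patient receives ("regardless of whether or not they took the IMP (but the treatment unit was provided to the outpatient"), which suggests a pack. The protocol's plural fits tablets or doses equally well. The rule fails to measure loss on either reading. If left over in SAP 6.2.3 meant dispensed minus taken, it would still flag a patient who returned every untaken tablet.
- **Counting tablets in the returned pack is part of the protocol's method.** The SAP keeps that source and drops the interview.

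A reader might infer that loss, even of a whole pack, leaves no trace in the outputs. The routes above show that this goes too far; what is missing is a summary of loss. A reader might also infer that the overall compliance percentage is wrong because it counts re-administered tablets over a fixed denominator. The documents do not support that: it is an explicit SAP definition, and SAP 6.2.2 reports re-administrations separately. Nor is Model 2 in SAP 8.7.2 affected, because Protocol 9.6.2 itself names tablets remaining as the quantity to relate to success.

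**Conclusion.** The rule is wrong as written for one secondary, descriptive feasibility endpoint. It repeats the compliance row exactly, and loss never triggers it. This follows from the SAP's own definitions and from the shared analysis set. The departure from the protocol is undeclared, although SAP 6.2.3 claims agreement with the protocol.

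The size in percentage points cannot be given, because the documents state neither the number of out-patients nor a loss rate. The per-patient arithmetic assumes one full pack and no other supply. The primary analysis is unaffected, and no hypothesis test depends on this row. The mismatch between 12 and 14 tablets is a separate erratum without numerical consequence.

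**What to change.** 1. Derive the mislaid endpoint from the Day 11 pack examination and interview: yes if the patient or caregiver reports loss, or if the pack is not returned because it was lost.
2. If a tablet balance is wanted as well, report dispensed minus reported taken (including re-administered) minus returned > 0, under the name of tablets unaccounted for. It also picks up recall error and discarded tablets, so it should not be called loss. Tablets taken must come from the interview or administration record; if they are inferred from the pack count, the balance is zero by construction.
3. If the CRF does not record loss, remove the duplicate row or relabel it as tablets returned, and state that loss was not assessed.
4. Declare the change in SAP 11 as made after database lock. SAP 11 already has an entry of that kind.
5. Separately, reconcile the expected tablet number below 35 kg between SAP 8.5 (12) and SAP 6.2.2 and 8.7.3 (14).

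The cost is wording in SAP 6.2.3 and 11, one re-derived, relabelled or removed row of Table 2.2.4.1, and one reconciled number. The CRF is not among the documents, so whether step 1 is possible has to be checked first. Step 3 needs no new data.
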